7.3.1.1.4 Safety Recommendations During the DBPCFC

As a safety precaution, the objective symptom(s) signalling the end of the DBPCFC will be treated by administration of the best medication(s) to the subject as per the Investigator's judgment. The Investigator and medical staff will use their own clinical judgment for the most effective treatment to give to the subject considering his/her age, the type of the allergic reactions and the severity of the allergic reaction. Also refer to recommendations made by Sampson et al for treating anaphylaxis.

Suggested treatments for the different objective symptoms will be detailed in the Manual of Procedures for the DBPCFC that will be provided to the sites. If there is a need to administer epinephrine to a subject, it should be injected intramuscularly in the anterolateral thigh. Epinephrine should NOT be administered i.v. at the investigative sites to treat the reactions, unless a subject is admitted into the Intensive Care Unit in a hospital setting to treat the severity of the reactions.

Subjects will be kept under observation for an additional 3 hours after the ingestion of the last dose of the challenge formula. Based on the Investigator's judgment, the observation period could be extended beyond 3 hours to ensure that all symptoms have subsided before the subject is discharged. For instance, an overnight stay may be considered necessary by the Investigator if the symptom(s) has (have) not completely resolved within the 3 hours or if the symptoms have been severe or serious and require longer observation periods.

7.3.1.2 Serum Immunology Markers

Blood samples will be collected from subjects to assess levels of sIgE and sIgG4 to cow's milk, caseins, α -lactalbumin, and β -lactoglobulin at the timepoints listed in the Schedule of Assessments ([Table 2 to Table 7](#)). Exploratory serum immunology markers are discussed below in [Section 7.3.3](#).

Blood samples for serum immunology markers will be analyzed at a central laboratory designated by the sponsor. Instructions for blood sample collection, storage, and shipment will be provided in the laboratory manual.

7.3.1.3 Skin Prick Test

SPTs will be performed at the visits listed in the Schedule of Assessments ([Table 2 to Table 7](#)). SPTs will be performed at all sites using the material recommended by the sponsor [CCI](#) to ensure consistency in the results. Cow's milk extract, plus negative control and positive control will be used for the SPT.

The subjects must not take antihistamines for 1 to 7 days (depending on the half-life; see [Appendix 14.7](#)) prior to the test. Briefly, a skin lancet is pressed through a small drop of the commercial extract of cow's milk and positive (histamine) and negative controls, into the epidermis of the volar surface of the forearm or back of the forearm. The area is measured for the average wheal diameter after 15 minutes. The average wheal diameter corresponds to the average of the size of the longest diameter and the longest perpendicular diameter. A tracing should be obtained by using a fine ballpoint pen. The tracing will be performed at the demarcation line for the wheal as the skin drops back to flush. Scotch or a clear transport tape should be used to lift the tracing and the tape tracing should be stuck in the subject's dossier.

The SPT should be performed by the same assessor at each visit, if possible, and the results will be recorded on the appropriate page(s) of the eCRF.

7.3.1.4 Quality of Life Questionnaire Forms

The QoL questionnaire FAQLQ/FAIM forms²³ was to be completed by the subjects (when applicable, depending on age) and parents/guardians at Screening Visit 1, at Month 12 and Month 24, and at Month 36 and Month 48 for subjects who entered the study extension ([Table 2](#), [Table 3](#), [Table 4](#), and [Table 5](#)). The QoL questionnaire will be completed at the time of the switch and after 6, 12, 18 and 24 months of treatment with Viaskin Milk 300 µg ([Table 6](#) and [Table 7](#)). At these visits, the QoL forms must be completed by the subjects (depending on the subject's age at the time of Visit 1) and parents/guardians before any other study procedures are performed on that day.

The appropriate QoL questionnaire forms to complete depend on the age of the subject at Visit 1, as follows:

- Subjects 8 to 12 years old at the time of Visit 1 will complete the form FAQLQ-CF (Child Form) at Screening (Visit 1) and at Month 12 and Month 24, and at Month 36 and Month 48 for subjects who entered the study extension. Subjects who are 7 years old at the time of Visit 1 may also complete the form FAQLQ-CF at Screening (Visit 1), if their parent(s)/guardians(s) consider they are able to complete these questionnaires, so that when they turn 8 years old at Month 12, they will have a baseline questionnaire available. However, this is not mandatory.
- Subjects 13 to 17 years old at the time of Visit 1 will complete the form FAQLQ-TF (Teenager Form) at Visit 1 and at Month 12 and Month 24, and at Month 36 and Month 48 for subjects who entered the study extension.
- Parents/guardians of subjects 0 to 12 years old at the time of Visit 1 will complete the form FAQLQ-PF at Visit 1 and at Month 12 and Month 24, and at Month 36 and Month 48 for subjects who entered the study extension.
- Parents/guardians of subjects 13 to 17 years old at the time of Visit 1 will complete the form FAQLQ-PFT at Visit 1 and at Months 12 and 24 and at Month 36 and Month 48 for subjects who entered the study extension.

The FAIM is included as a part of the questionnaires listed above. The QoL questionnaire forms are included in [Appendix 14.3](#).

Data collected in the QoL forms must be entered on the appropriate pages of the eCRF. In order to maintain an unbiased assessment, the Investigator or study site

personnel must not influence the subject and/or parent(s)/guardian(s) while they are completing the forms.

7.3.2 Safety Assessments

Safety assessments will include the following:

- AEs (including Viaskin Milk-induced local AEs and SAEs)
- Vital Signs
- Physical examinations (including complete skin examination)
- Clinical laboratory data
- Spirometry and PEF data

7.3.2.1 Adverse Events

7.3.2.1.1 Definitions of an Adverse Event

An AE is defined as any untoward medical occurrence in a clinical study subject administered a medicinal product and which does not necessarily have a causal relationship with this treatment. An AE can therefore be any unfavourable and unintended sign (including an abnormal laboratory finding or vital sign measurement), symptom, or disease temporally associated with the use of a medicinal (investigational) product, whether or not related to the medicinal (investigational) product.²⁴ This includes an exacerbation of pre-existing conditions or events, intercurrent illnesses, drug interaction or the significant worsening of the indication under investigation that is not recorded elsewhere in the eCRF under specific efficacy assessments. Note: A procedure is not an AE, but the reason for the procedure may be an AE.

It is the responsibility of the Investigators to document all AEs that occur during the study. AEs will be elicited by asking the subject or his/her parent(s)/guardian(s) a nonleading question, for example, "Are there any new or changed symptoms since we last asked or since your last visit?" AEs should be reported on the appropriate page of the eCRF.

All AEs occurring after the first Viaskin patch application will be considered treatment-emergent AEs (TEAEs). TEAEs will be defined as any AEs, regardless of relationship to Investigational product, which occur during or after the initial Viaskin patch application or any event already present that worsens in either intensity or frequency following exposure to the Viaskin patch. If relationship information is missing for a TEAE, it will be considered drug-related. AEs with missing or incomplete onset date will be treated as TEAEs and missing onset date will be imputed as date of initial Viaskin patch application unless there is evidence that the event occurred before the treatment period.

Assessment of Severity

Each AE will be assigned a category by the Investigator as follows:

Mild An AE that is easily tolerated by the subject, causes minimal discomfort and does not interfere with everyday activities.

Moderate An AE that is sufficiently discomforting to interfere with normal everyday activities; intervention may be needed.

Severe An AE that prevents normal everyday activities; treatment or other intervention may be needed.

If there is a change in severity of an AE, it must be recorded as a separate event.

The severity of anaphylactic reactions, including those reported as part of medical history, will be assessed using the Anaphylaxis Staging System ([Appendix 14.4](#)). For anaphylactic reactions occurring during the DBPCFC, only those considered to be a SAE will be assessed for severity.

Assessment of Causality

The relationship between an AE and the investigational product will be determined by the Investigators on the basis of his/her clinical judgment and the following definitions:

Unrelated	Clinical event with an incompatible time relationship to the investigational product administration, and that could be explained by underlying disease or other drugs or chemicals or is incontrovertibly not related to the investigational product.
Unlikely	Clinical event whose time relationship to the investigational product administration makes a causal connection improbable, but that could plausibly be explained by underlying disease or other drugs or chemicals.
Possible	Clinical event with a reasonable time relationship to the investigational product administration, but that could also be explained by concurrent disease or other drugs or chemicals.
Probable	Clinical event with a reasonable time relationship to the investigational product administration, and is unlikely to be attributed to concurrent disease or other drugs or chemicals.
Definite	Clinical event with plausible time relationship to the investigational product administration, and that cannot be explained by concurrent disease or other drugs or chemicals.

All SAEs assessed as “definitely related”, “probably related” and “possibly related” will be categorized as “related” for expedited reporting.

Action Taken

The Investigators will describe the action taken with the drug product in the appropriate section of the eCRF, as follows:

- None: No change in the dose of the study product.
- Discontinued permanently: The study product was permanently stopped.
- Temporarily interrupted: Dosing of the study product was interrupted.
- Other: Specify.

Outcomes of Adverse Events

The Investigators will describe the outcome of the AEs in the appropriate section of the eCRF, as follows:

- Recovered/Resolved: The subject fully recovered from the AE with no residual effect observed.
- Recovered/Resolved with sequelae: The residual effects of the AE are still present and observable.
- Ongoing: The AE itself is still present and observable.
- Death.
- Unknown/Lost to follow up.

Treatment Required

The Investigators will describe if the subject was treated for an AE in the appropriate section of the eCRF, as follows:

- None: No treatment was required.
- Medication required: Prescription and/or over-the-counter medication were required to treat the AE.
- Hospitalization or prolongation of hospitalization required: Hospitalization was required or prolonged due to the AE, whether or not medication was required.
- Other: Specify.

More than one option can be recorded to report all treatments given for each AE.

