7.3.2.1.2 Reporting and Follow-up of Adverse Events

AEs will be reported and documented in accordance with the procedures outlined in this section. AEs will be reported from the time of informed consent through to the EOS visit and documented on the appropriate AE pages of the eCRF.

The Investigator will be responsible for ensuring that correct information concerning all AEs is included on the appropriate pages of the eCRF.

The following data should be documented for each AE:

Diagnosis of the event if available and description of the symptom event.

Classification of 'serious' or 'not serious.'

Severity.

Date of first occurrence and date of resolution (if applicable).

Action taken.

Treatment required.

Causal relationship.

Outcome of event (recovered, recovered with sequelae, ongoing, death [with date and cause reported], unknown).

All Investigators should follow up subjects with AEs until the event is resolved or until, in the opinion of the Investigator, the event is stabilized or determined to be chronic. Details of AE resolution must be documented in the eCRF.

Based on the medical judgment of the Investigator, all non-serious AEs (including the abnormal laboratory values identified as AEs by the Investigator) will be followed until

30 days after the removal of the last Viaskin patch. All unresolved, nonserious AEs beyond such date will be recorded as “ongoing” without further follow-up.

7.3.2.2 **Serious Adverse Events**

7.3.2.2.1 **Serious Adverse Event Definition**

An SAE is any untoward medical occurrence or effect that, at any dose:

- Results in death.
- Is life-threatening. This means that the subject is at risk of death at the time of the event; it does not mean that the event might hypothetically have caused death if it was more severe.

Note: Whereas an anaphylactic reaction is generally considered to be potentially life-threatening, not all anaphylaxes put the subjects at immediate risk of death, if for example appropriate treatments lead to symptoms reduction or disappearance. As per the Anaphylaxis Staging System classification ([Appendix 14.4](#)), an anaphylaxis assessed as mild or moderate should not be classified as life-threatening.

- Requires hospitalization (at least overnight stay or inpatient hospital admission) or prolongation of existing hospitalization

Events associated with **hospitalization** for the following reasons will **not** be considered as a SAE:

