9.3 ADVERSE EVENTS

9.3.1 Definitions

Treatment emergent AEs (TEAEs) are defined as any AEs, regardless of relationship to investigational product which occur during or after the initial patch application (or any event already present that worsens in intensity following exposure to the patch).

AEs with missing or incomplete onset date will be treated as TEAEs and missing onset date will be imputed as date of initial patch application unless there is evidence that the event occurred prior or after the treatment period, e.g. year and month indicate the onset date is before study treatment.

AEs will be considered drug-related if relationship information is definite / probable / possible. If relationship information is missing for a TEAE, the AE will be considered as drug-related.

This document is confidential

Statistical Analysis Plan

If the severity is missing of an AE starting prior to the date of initial patch application, then a severity of "Mild" will be assigned. If the severity is missing of an AE starting on or after the date of initial patch application, then a severity of "Severe" will be assigned.

Imputed values for relationship, severity or onset date will be used for incidence summaries, while the actual values will be used in data listings.

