12.5 AMENDMENT 5: FINAL VERSION 5.0, 15 MAY 2018

Following study design change implemented in protocol amendment 5, dated 15 May

This document is confidential

Statistical Analysis Plan

2018, to allow all study subjects to switch from Viaskin Milk 500 μ g to Viaskin Milk 300 μ g for a 24 months treatment period, no change between applicable protocol and current SAP version.

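### The SAP drops worsening in frequency from the protocol's TEAE definition without declaring it, and the protocol has no rule for recording such worsening

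*Protocol*

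**What the plan says.** Protocol section 7.3.2.1.1 gives two routes to a TEAE. One is onset: an AE that starts with or after the first patch. The other is worsening of something already there: "any event already present that worsens in either intensity or frequency following exposure to the Viaskin patch". The same section sets a recording rule: "If there is a change in severity of an AE, it must be recorded as a separate event". It gives no such instruction for a change in how often an event occurs. Section 7.3.2.1.2 lists what is documented for each AE: diagnosis or description, seriousness, severity, start and end dates, action taken, treatment, causality and outcome. Frequency is not among them.

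SAP section 9.3.1 keeps the onset route, for AEs "which occur during or after the initial patch application". Its worsening route reads "or any event already present that worsens in intensity following exposure to the patch". SAP section 12, which records changes from the protocol-planned analysis, does not mention this under any amendment. Section 12.5 states "no change between applicable protocol and current SAP version", and section 12.6 reports no change for Amendment 6.

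**The concern.** SAP 9.3.1 is the general definition behind the TEAE overviews, the incidence tables, the related-TEAE tables and the subject-year analyses in SAP 9.3.3 and 9.3.4. A narrower definition there carries through all of them. It can only remove events that the protocol calls treatment-emergent; it cannot add any.

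The population makes the point relevant. These are children with milk allergy, and SAP 7.2.1 summarises asthma, atopic dermatitis and allergic rhinitis in the medical history. An intermittent event that recurs more often at an unchanged grade is a form of worsening that the protocol intends to count. Frequency is not a stray word there: the hospitalisation exemption in protocol 7.3.2.2.1 also requires that a pre-existing condition has worsened in neither severity nor frequency. A reader who takes SAP section 12 at its word would assume that the TEAE tables follow the protocol on this point.

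**Working it through.** The plan gives no figure to reproduce: neither document counts AEs open at first patch or describes their frequency. The check is therefore textual. It uses the two definitions above and three further inputs.

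- **What counts as an AE.** Protocol 7.3.2.1.1 says of the AE definition: "This includes an exacerbation of pre-existing conditions or events". A flare of a known condition is thus an AE in its own right.
- **When AE collection starts.** AEs are recorded from consent at Visit 1, and the screening period up to Visit 4 is at most 60 days (protocol 7.2.1 and 7.2.1.1). An AE record can therefore be open at first patch.
- **How continuing events are assigned to periods.** SAP 6.4 assigns an AE that runs from the blinded into the open-label period only to the period in which it appeared or worsened. It does not define worsened.

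Taking the possible cases in turn:

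1. *A discrete flare after the first patch, entered with its own onset date.* TEAE under both documents by the onset route, at any grade.
2. *A condition known from medical history, with no AE open at first patch, that flares later.* The exacerbation is an AE with post-patch onset, so this reduces to case 1.
3. *An AE record open at first patch whose severity then rises.* A separate record is mandatory, and both worsening routes apply. TEAE under both.
4. *An AE record opened between consent and first patch, still open at first patch and kept as one record, whose frequency alone rises.* TEAE under the protocol, not under the SAP. No rule requires a new record, and no listed item would show the change.
5. *An AE with onset in the blinded period that continues into open-label treatment and becomes more frequent.* Already a TEAE under both. If worsened in SAP 6.4 is read as in 9.3.1, the event stays in the blinded period and the increase does not appear in the open-label tables.

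Only case 4 changes TEAE status between the two documents. Case 5 affects period assignment, not TEAE status.

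**The case against.** The best case on the other side is that this is a difference of one phrase with little practical effect. A reader might infer that more frequent attacks on the patch vanish from the TEAE tables, or that the AE form opens a new record only when severity changes. The documents support neither inference. Post-patch attacks entered as separate AEs are kept by the onset route in both documents. The severity sentence makes a new record mandatory in one situation and does not bar one in others. The case report form itself is not in the documents.

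Other displays also give partial cover. The blinded-period AE overview includes screening (SAP 9.3.3.1). Diary itching, redness and swelling are counted in days by severity for the first three months (SAP 9.10.2). Physical examination, patch-site skin grades and lung function are summarised by visit.

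These arguments stand, and they confine the problem to case 4 and the period assignment in case 5. They do not remove the mismatch. Both definitions are current text, and section 12 is used for small AE wording changes (12.2 c), so silence there is not a matter of scale. None of the other displays identifies case 4 as treatment-emergent.

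A further objection is that restoring the word does little unless frequency is recorded. That is right, and it is why the fix needs a recording instruction as well.

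**Conclusion.** The concern holds in a limited form. SAP 9.3.1 is narrower than protocol 7.3.2.1.1, the change is undeclared, and the statement in SAP 12.5 is inaccurate on this point. The events that lose TEAE status are AE records opened between consent and first patch, still open at first patch, whose frequency alone rises.

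Their number cannot be estimated from the documents. A subject with another TEAE is still counted in the any-TEAE row, so the effect falls mainly on event counts and on rows by preferred term. Relative to the protocol, the SAP can only under-count. A reader might go on to infer that the comparison with placebo is biased towards no harm. That would require a real effect of active patches on frequency, which the documents do not show. Primary efficacy is unaffected.

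The conclusion assumes that sites enter post-patch flares as separate AEs, as the AE definition implies. It also assumes that the blinded-period analysis used the rule now printed in SAP 9.3.1. SAP section 2 says that the analyses of versions 4.0 to 6.0 are retained in the current document, with only the definition of AEs of specific interest noted as updated.

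**What to change.** - **SAP 9.3.1:** restore worsening in intensity or frequency, to match the protocol.
- **SAP 6.4:** state that worsened has the same meaning when continuing AEs are assigned to a period.
- **Protocol 7.3.2.1.1:** next to the severity rule, add that a rise in frequency of an event already present is entered as a separate AE with its own onset date.
- **Timing:** apply these changes prospectively to what remains of the open-label periods.
- **Blinded period:** state in the report that its TEAE tables used the intensity-only rule, after confirming this against SAP version 4.0. Do not reclassify blinded-period events. SAP 11.1 records that this database was locked, unblinded and reported in the 12-month report. With no frequency item among the listed AE data, reclassification would rest on judgement made with treatment known.

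The cost is a few words in the SAP, one recording instruction in the protocol, a few more AE records and a slightly higher TEAE count. The change cannot improve the placebo-controlled comparison, which is already complete.

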7.3.2.1.2 Reporting and Follow-up of Adverse Events

AEs will be reported and documented in accordance with the procedures outlined in this section. AEs will be reported from the time of informed consent through to the EOS visit and documented on the appropriate AE pages of the eCRF.

The Investigator will be responsible for ensuring that correct information concerning all AEs is included on the appropriate pages of the eCRF.

The following data should be documented for each AE:

Diagnosis of the event if available and description of the symptom event.

Classification of 'serious' or 'not serious.'

Severity.

Date of first occurrence and date of resolution (if applicable).

Action taken.

Treatment required.

Causal relationship.

Outcome of event (recovered, recovered with sequelae, ongoing, death [with date and cause reported], unknown).

All Investigators should follow up subjects with AEs until the event is resolved or until, in the opinion of the Investigator, the event is stabilized or determined to be chronic. Details of AE resolution must be documented in the eCRF.

Based on the medical judgment of the Investigator, all non-serious AEs (including the abnormal laboratory values identified as AEs by the Investigator) will be followed until

30 days after the removal of the last Viaskin patch. All unresolved, nonserious AEs beyond such date will be recorded as “ongoing” without further follow-up.

7.3.2.2 **Serious Adverse Events**

7.3.2.2.1 **Serious Adverse Event Definition**

An SAE is any untoward medical occurrence or effect that, at any dose:

- Results in death.
- Is life-threatening. This means that the subject is at risk of death at the time of the event; it does not mean that the event might hypothetically have caused death if it was more severe.

Note: Whereas an anaphylactic reaction is generally considered to be potentially life-threatening, not all anaphylaxes put the subjects at immediate risk of death, if for example appropriate treatments lead to symptoms reduction or disappearance. As per the Anaphylaxis Staging System classification ([Appendix 14.4](#)), an anaphylaxis assessed as mild or moderate should not be classified as life-threatening.

- Requires hospitalization (at least overnight stay or inpatient hospital admission) or prolongation of existing hospitalization

Events associated with **hospitalization** for the following reasons will **not** be considered as a SAE:

1. Evaluation or treatment of a pre-existing (before informed consent signature) and non-exacerbating condition:

- a. The condition existed prior to the subject's entry into the study and has been recorded in the subject's disease/medical history and the e-CRF **AND**
- b. The condition has not worsened in severity or frequency during the subject's exposure to the investigational product **AND**
- c. It has not required a change in treatment management during the subject's exposure to the investigational product;

2. Hospitalization for a planned treatment of a pre-existing (before informed consent signature) and non-exacerbating condition;

3. Hospitalization the day prior to or after the day of DBPCFC for practical reasons and without any AE fulfilling any other seriousness criterion.

- Results in persistent or significant disability/incapacity (an AE is incapacitating or disabling if it results in a substantial and/or permanent disruption of the subject's ability to carry out normal life functions).

- Is a congenital anomaly/birth defect.

- Is an **“important medical event”** that may not be immediately life-threatening or result in death or hospitalization but that may jeopardize the subject or require intervention to prevent one of the above outcomes. Examples of such events are intensive treatment in an emergency room or at home for allergic bronchospasm; blood dyscrasias or convulsions that do not result in hospitalization; or development of drug dependency or drug abuse.

- An anaphylactic reaction classified as severe using the Anaphylaxis Staging System in [Appendix 14.4](#) (i.e., anaphylactic reaction with cyanosis or SpO2

≤92%, hypotension with >20% drop in blood pressure, confusion, collapse, loss of consciousness or incontinence) or requiring 3 or more epinephrine uses should be reported as an “important medical event”

- In the context of DBPCFC, in addition to severe anaphylaxis, the occurrence of:
 - Bronchospasm/audible wheezing with use of accessory muscles,
 - Severe angioedema,
 - Admission in intensive care unit and/or requirement of oxygen therapy,
 - Intake of 3 or more doses of epinephrine

should be considered as meeting the seriousness criterion of “important medical event”.

All SAEs occurring after the start of Viaskin patch application will also be defined as treatment-emergent SAEs (TESAEs).

